**Severe Calcification:**

By angiography: presence of radiopacities noted without cardiac motion prior to contrast injection usually involving both sides of the arterial wall in at least one (1) location, with total length of calcium (including segmented)  $\geq 15$  mm and extending partially into the target lesion.

By OCT: presence of  $\geq 180^\circ$  of calcium in at least one (1) cross section with minimal thickness  $>0.5$ mm.

**Intraprocedural stent thrombosis:** new or increasing thrombus developing within or adjacent to the stent during the index PCI procedure

**Stent Thrombosis (definite or probable; modified ARC definitions):**

Acute stent thrombosis (\*): from completion of PCI procedure to 24 hours after stent implantation

Subacute stent thrombosis (\*):  $>24$  hours – 30 days after stent implantation

Late stent thrombosis (\*\*):  $>30$  days – 1 year after stent implantation

Very late stent thrombosis (\*\*):  $>1$  year after stent implantation

(\*) acute or subacute can also be replaced by the term early stent thrombosis.

(\*\*) including 'primary' as well as 'secondary' late stent thrombosis; 'secondary' late stent thrombosis is a stent thrombosis after a target lesion revascularization.

**Stent Thrombosis, Definite\*:**

Definite stent thrombosis is considered to have occurred by either angiographic or pathological confirmation.

Angiographic confirmation of stent thrombosis

The presence of a thrombus that originates in the stent or in the segment 5 mm proximal or distal to the stent AND presence of at least 1 of the following criteria within a 48-hour

time window:

- Acute onset of ischemic symptoms at rest

- New ischemic ECG changes that suggest acute ischemia
- Typical rise and fall in cardiac biomarkers (refer to definition of spontaneous MI)

\*The incidental angiographic documentation of stent occlusion in the absence of clinical signs or symptoms is not considered a confirmed stent thrombosis (silent occlusion).

**Stent Thrombosis, Probable:**

Clinical definition of probable stent thrombosis is considered to have occurred after intracoronary stenting in the following cases:

- Any unexplained death within the first 30 days.
- Irrespective of the time after the index procedure, any MI that is related to documented acute ischemia in the territory of the implanted stent without angiographic confirmation of stent thrombosis and in the absence of any other obvious cause.

**Successful and Uncomplicated:**

For non-target lesion treatment during the index procedure, defined as angiographic diameter stenosis <10% for all treated non-target lesions, with TIMI III flow in this vessel, without final dissection  $\geq$  NHLBI type B, perforation anytime during the procedure, prolonged chest pain (>5 minutes) or prolonged ST-segment elevation or depression (>5 minutes), or cardiac arrest or need for defibrillation or cardioversion or hypotension/heart failure requiring mechanical or intravenous hemodynamic support or intubation).

**Target Lesion:** The target lesion is the treated lesion starting 5mm proximal to the stented lesion and ending 5mm distal to the stented lesion.

**Target Lesion Failure (TLF):** The composite of cardiac death, target vessel related myocardial infarction, or ischemia-driven target lesion revascularization.

**Target Lesion Revascularization (TLR):** Repeat revascularization of the target lesion.

**Target Vessel Failure (TVF):** The composite of cardiac death, target vessel related myocardial infarction, or ischemia driven target vessel revascularization.

**Target Vessel Revascularization (TVR):** Repeat revascularization of the target vessel (inclusive of the target lesion).

**Ischemia-Driven [ID] Revascularization (TLR/TVR):** A revascularization is considered ischemia driven if associated with any of the following:

- Positive functional ischemia study including positive FFR, iFR, etc.
- Ischemic symptoms and angiographic diameter stenosis  $\geq$ 50% by core laboratory QCA
- Angiographic diameter stenosis  $\geq$  70% by core laboratory QCA without angina or positive functional study

**COVID-19 Relatedness Definitions**

The COVID-19 relatedness to an adverse event, is adjudicated by the CEC committee into 3 categories: likely related, possibly related, or not likely related, based on the COVID-19 relatedness definitions that are described on the CEC charter. Please refer to the CEC charter for the COVID-19 relatedness definitions.

**Thrombolysis In Myocardial Infarction (TIMI) Flow Grading System:**

Grade 0 (no perfusion): There is no antegrade flow beyond the point of occlusion.

Grade 1 (penetration without perfusion): The contrast material passes beyond the area of obstruction but “hangs up” and fails to opacify the entire coronary bed distal to the obstruction for the duration of the cineangiographic filming sequence.

Grade 2 (partial perfusion): The contrast material passes across the obstruction and opacifies the coronary bed distal to the obstruction. However, the rate of entry of contrast material into the vessel distal to the obstruction or its rate of clearance from the distal bed (or both) is perceptibly slower than its entry into or clearance from comparable areas not perfused by the previously occluded vessel (e.g., the opposite coronary artery or the coronary bed proximal to the obstruction).

Grade 3 (complete perfusion): Antegrade flow into the bed distal to the obstruction occurs as promptly as antegrade flow into the bed from the involved bed and is as rapid as clearance from an uninvolved bed in the same vessel or the opposite artery.

**Thrombus, Nonocclusive:** Intracoronary thrombus is defined as a (spheric, ovoid or irregular) non-calcified filling defect or lucency surrounded by contrast material (on 3 sides or within a coronary stenosis) seen in multiple projections, or persistence of contrast material within the lumen, or a visible embolization of intraluminal material downstream.

**Thrombus, Occlusive:** TIMI 0 or TIMI 1 intra-stent or proximal to a stent up to the most adjacent proximal side branch or main branch (if originates from the side branch).

**Appendix C: Labels**

[Redacted content]

**Appendix D: Case Report Form**

[Redacted]

[Redacted]

## Appendix F: Pre-specified Powered Analysis of XIENCE in the In-Stent Restenosis (ISR) Population

### Introduction

Abbott is evaluating the safety and effectiveness of treating in-stent restenosis (ISR) lesions with the XIENCE family of stents within the ILUMIEN IV trial. The trial enrolls patients undergoing planned XIENCE stent implantation during a clinically indicated PCI procedure who satisfy the eligibility criteria described in **Section 5.4** of this CIP. A pre-specified powered analysis of XIENCE is being conducted in randomized ILUMIEN IV subjects with ISR and is described below. The XIENCE ISR analysis is intended to support an indication expansion for treatment of ISR lesions with the XIENCE family of stents in the USA.

The XIENCE ISR analysis is independent of the main ILUMIEN IV study objective outlined in **Section 1.1** of the CIP, which is to demonstrate the superiority of an OCT-guided stent implantation strategy as compared to an angiography-guided stent implantation strategy.

### Objective

The objective of the XIENCE ISR analysis is to demonstrate the safety and effectiveness of XIENCE in the treatment of ISR lesions.

### Analysis Population

The XIENCE ISR analysis population is comprised of randomized subjects pooled from both study arms and enrolled under the ILUMIEN IV regulated protocol [REDACTED] or the post-market protocol [REDACTED], who have had at least one XIENCE stent implanted in an ISR target lesion.

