### **6.5.3.5 Assessment of the Target Lesion Length by OCT**

The proximal and distal reference segments are initially identified by angiography, and then confirmed by performing pre-procedural OCT pullback across the target segment (**Figure 1a**). In cases in which a severe stenosis would interfere with distal clearance of blood, or if the lumen border at both (proximal and distal) reference segments cannot be detected by OCT, vessel preparation is strongly recommended with balloon dilatation or other modalities (e.g. cutting balloon, atherectomy, thrombectomy, etc.) deemed necessary by the operator, followed by OCT.

When the lumen borders at both reference segments can be measured, the reference sites will be decided by the position with the largest lumen using the OCT Lumen Profile software, where sufficient external elastic lamina is visible to allow measurement of stent diameter, typically several mm away from the angiographic lesion shoulders. If sufficient EEL cannot be visualized at the initially chosen reference cross-section, the reference cross-section is adjusted  $\pm 5$  mm to identify a cross-section where the EEL is visible sufficient to allow stent diameter measurement. The stent length will be determined by measuring from the distal to the proximal reference site using the OCT Lumen Profile software. A XIENCE stent of appropriate length should be selected to be implanted in these reference segments if possible. See example in **Figure 4**. If a XIENCE stent of the appropriate length is commercially available but not in stock at the study site, a competitive DES of the appropriate length must be used and a protocol deviation must be recorded. Overlapping XIENCE stents must only be used for planned treatment of long lesions where a XIENCE stent of appropriate length is not commercially available.

**Figure 1a. Procedure for OCT-guided stent implantation.** Vessel diameter must be assessed by the EEL-EEL diameter at the reference segment unless the EEL cannot be identified there.

[figure not shown]
[figure not shown]
[figure not shown]

Figure 1b. Procedure for post-implant stent optimization per EEL diameter and per lumen diameter

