### Endpoints

The primary endpoint for the XIENCE ISR analysis is target lesion failure (TLFISR). TLFISR is the event rate of the composite outcome of cardiac death, target vessel myocardial infarction (TV-MI) (per primary protocol definition [see Appendix B]), or ischemia-driven target lesion revascularization (ID-TLR), assessed at 1 year.

Non-powered secondary endpoints for the XIENCE ISR analysis to be assessed at 1 year are as follows:

1. Cardiac deathISR
2. TV-MIISR
3. ID-TLRISR
4. Stent thrombosisISR
5. All-cause mortalityISR

In addition, the following outcomes will be reported as sensitivity analyses at 1 year:

6. TV-MIISR,SCAI (periprocedural MI by SCAI definition and spontaneous MI by protocol definition)
7. Periprocedural MIISR,SCAI (by SCAI definition)
8. All MIISR,SCAI (periprocedural MI by SCAI definition and spontaneous MI by protocol definition)
9. TLFISR,SCAI; the composite of cardiac death, TV-MIISR,SCAI or ID-TLR

Note: In the XIENCE ISR analysis population, TV-MIISR and TV-MIISR,SCAI include MI events with confirmed target vessel involvement and indeterminate vessel MI events.

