**Statistical Considerations**

The hypothesis for the XIENCE ISR analysis is as follows:

$H_0$ :  $TLF_{ISR} \geq PG$

$H_a$ :  $TLF_{ISR} < PG$ ,

The null hypothesis will be tested using a one-sided alpha of 2.5%.

For subjects with multiple target vessels,  $TLF_{ISR}$  in any vessel with at least one XIENCE stent implanted on an ISR target lesion constitutes an endpoint event.

The primary endpoint  $TLF_{ISR}$  is assessed to evaluate the safety and effectiveness of XIENCE in ISR lesions. This endpoint must be met to demonstrate success for XIENCE in ISR lesions.

Details on subgroup analyses of the XIENCE ISR primary endpoint  $TLF_{ISR}$  can be found in the separate Statistical Analysis Plan (SAP).

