APPENDIX C: Pre-specified Powered Analysis of XIENCE in the In-Stent Restenosis (ISR) Population

Introduction

Abbott is evaluating the safety and effectiveness of treating in-stent restenosis (ISR) lesions with the XIENCE family of stents within the ILUMIEN IV trial. The trial enrolls patients undergoing planned XIENCE stent implantation during a clinically indicated PCI procedure who satisfy the eligibility criteria described in **Section 5.4** of the CIP. A pre-specified powered analysis of XIENCE is being conducted in randomized ILUMIEN IV subjects with ISR and is described below. The XIENCE ISR analysis is intended to support an indication expansion for treatment of ISR lesions with the XIENCE family of stents in the USA. The XIENCE ISR analysis will be conducted after the last enrolled patient reaches 2 years of follow-up.

The XIENCE ISR analysis is independent of the main ILUMIEN IV study objective outlined in **Section 1.1** of the CIP, which is to demonstrate the superiority of an OCT-guided stent implantation strategy as compared to an angiography-guided stent implantation strategy.

Objective

The objective of the XIENCE ISR analysis is to demonstrate the safety and effectiveness of XIENCE in the treatment of ISR lesions.

Analysis Population

[REDACTED]

Primary Endpoint

The primary endpoint for the XIENCE ISR analysis is target lesion failure (TLF_{ISR}). TLF_{ISR} is the event rate of the composite outcome of cardiac death, target vessel myocardial infarction (TV-MI) (per primary protocol definition in Appendix B), or ischemia-driven target lesion revascularization (ID-TLR), assessed at 1 year. For subjects with multiple target vessels, TLF_{ISR} in any vessel with at least one XIENCE stent implanted on an ISR target lesion constitutes an endpoint event. The primary endpoint TLF_{ISR} is assessed to evaluate the safety and effectiveness of XIENCE in ISR lesions. This endpoint must be met to demonstrate success for XIENCE in ISR lesions.

[REDACTED]

Abbott

Study Name: ILUMIEN IV

Statistical Analysis Plan

Statistical Considerations

The hypothesis for the XIENCE ISR analysis is as follows:

$$H_0: TLF_{ISR} \geq PG$$

$$H_a: TLF_{ISR} < PG$$

where PG (performance goal) equals 20%. The null hypothesis will be tested using a one-sided alpha of 2.5%.

Sample Size and Power

A sample size of 228 subjects will provide approximately 90% power to reject the null hypothesis

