For the determination of binary event rates at time points such as 1 year, the denominators are defined as below based on the type of events.

- Death/MI/Revascularization (DMR) event

Subjects will be included in the analysis if they either had the DMR event by the analysis time point or they did not have the DMR event but had follow-up visit falling into the specific window. In other words, subjects will be included in a given analysis if it can be determined whether or not the subject would have had the DMR event by the time point.

- Special events such as Stent Thrombosis (ST)

Subjects will be included in the analysis if they either had the specific event (for example, for analysis on ST, only ST is considered) by the analysis time point or they did not have the event but had follow-up visit falling into the specific window. In other words, subjects will be included in a given analysis if it can be determined whether or not the subject would have had the specific event by the time point.

Abbott

Study Name: ILUMIEN IV

Statistical Analysis Plan

Subgroup Analyses

Subgroup analyses will be performed to examine the consistency of TLF_{ISR} across study subgroups for the following baseline variables:

- Gender: male vs. female
- Age (e.g., < 65 , ≥ 65)
- Race (all categories as well as white vs non-white)
- Ethnicity (Hispanic or Latino vs not Hispanic or Latino)
- ACS vs. non-ACS
- Diabetes vs. non-diabetes
- Long or multiple lesions (defined as intended total stent length in any single target vessel ≥ 28 mm) vs. short and single lesions
- Bifurcations: yes vs. no
- Angiographic severe calcification vs. non-calcification
- OCT-guided treatment vs. angiography-guided treatment
- Medication-treated diabetes mellitus vs. others

Poolability Analysis

Non-powered Secondary Endpoints

Non-powered secondary endpoints for the XIENCE ISR analysis to be assessed at 1 year are as follows:

1. Cardiac death $_{ISR}$

Statistical Analysis Plan

- 2. TV-MI_{ISR}
- 3. ID-TLR_{ISR}
- 4. Stent thrombosis_{ISR}
- 5. All-cause mortality_{ISR}

In addition, the following outcomes will be reported as sensitivity analyses at 1 year:

- 6. TV-MI_{ISR,SCAI} (periprocedural MI by SCAI definition and spontaneous MI by protocol definition)
- 7. Periprocedural MI_{ISR,SCAI} (by SCAI definition)
- 8. All MI_{ISR,SCAI} (periprocedural MI by SCAI definition and spontaneous MI by protocol definition)
- 9. TLF_{ISR,SCAI}; the composite of cardiac death, TV-MI_{ISR,SCAI} or ID-TLR

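### The XIENCE in-stent restenosis goal test counts only subjects who received a XIENCE in such a lesion, so a XIENCE attempt that fails entirely leaves both numerator and denominator

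*Protocol*

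**What the plan says.** Protocol Appendix F describes an analysis meant to show that XIENCE is safe and effective in ISR lesions and to support a wider US indication. It pools both randomized arms and keeps subjects "who have had at least one XIENCE stent implanted in an ISR target lesion". The endpoint combines cardiac death, target vessel MI and "ischemia-driven target lesion revascularization (ID-TLR), assessed at 1 year". For subjects with several target vessels, Appendix F and SAP Appendix C both tie the event to a vessel in which a XIENCE was implanted on an ISR target lesion.

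SAP Appendix C sets the goal at 20%, uses a one-sided 2.5% test and states: "A sample size of 228 subjects will provide approximately 90% power to reject the null hypothesis".

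Three other places bear on the point:

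- **Entry.** Protocol 5.4.1, criterion 3, admits patients by planned XIENCE implantation.
- **Main clinical endpoint.** Protocol 7.1.2.3 analyses TVF by intention to treat, whatever device was attempted or implanted. SAP 5.5.1 does the same for the secondary endpoints.
- **Routes to no XIENCE.** When a suitable XIENCE is out of stock, protocol 6.5.3.5 says that "a competitive DES of the appropriate length must be used and a protocol deviation must be recorded"; 6.5.3.4 has a similar rule for diameter. Protocol 6.5.3.4 and 6.5.3.7 also cover balloon-only treatment of ISR when OCT shows that underexpansion is the main mechanism.

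SAP Appendix C lists "OCT-guided treatment vs. angiography-guided treatment" among the subgroups used to examine the consistency of TLF_ISR.

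**The concern.** A claim about treating ISR with XIENCE normally starts from the decision or attempt to use it. Here the set starts from success in placing it. A subject in whom delivery fails completely, and who is then treated with something else or not at all, is removed together with any periprocedural MI, revascularization or death. Those are components of the endpoint. In a randomized comparison both arms might lose such subjects. Against a fixed goal, nothing balances the loss.

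There is a second, smaller issue. The stock-out and balloon-only provisions sit in the OCT-guidance instructions, and the balloon-only route depends on an OCT finding. Selection into the implanted set can therefore differ by arm, and the OCT-versus-angiography contrast inside it does not compare the groups as randomized.

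At stake is whether meeting the goal describes XIENCE treatment of ISR or only XIENCE once it is in place.

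**Working it through.** **Inputs from the documents:** goal p0 = 0.20, one-sided alpha = 0.025, n = 228, power about 90% (SAP Appendix C). The visible text does not name the test or give the expected TLF rate. I use an exact binomial test and note where another choice matters.

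**Step 1. The plan's own figure.** The exact test passes when X ≤ c, where c is the largest count with P(X ≤ c | n, 0.20) ≤ 0.025. For n = 228, c = 33 (33/228 = 14.5%), with P = 0.0196; 34 events give 0.0298. The 228/90% statement cannot be reproduced without the expected rate, so I solved for the rate it implies: 11.9% (exact), 12.0% (normal, null variance) or 12.8% (Wald). A rate of 12% gives 89.2%, 90.4% and 96.1% power respectively. The stated figure is thus consistent with an expected rate of about 12% under the first two methods.

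**Step 2. False-pass probability.** Let m excluded attempts have event rate q, and N = 228 + m. Set the true all-attempted rate at the goal. The implanted rate is then (0.20·N − m·q)/228, and the pass probability is P(X ≤ 33 | 228, that rate). Both m and q are assumptions.

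| Excluded | q | Implanted rate | P(pass) |
|---|---|---|---|
| 5 of 233 (2%) | 30% | (46.6 − 1.5)/228 = 19.8% | 2.4% |
| 5 of 233 (2%) | 40% | (46.6 − 2.0)/228 = 19.6% | 2.9% |
| 12 of 240 (5%) | 30% | (48.0 − 3.6)/228 = 19.5% | 3.1% |
| 12 of 240 (5%) | 40% | (48.0 − 4.8)/228 = 18.9% | 4.7% |
| 25 of 253 (10%) | 30% | (50.6 − 7.5)/228 = 18.9% | 4.9% |
| 25 of 253 (10%) | 40% | (50.6 − 10.0)/228 = 17.8% | 10.8% |

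If q equals the implanted rate (20%), the pass probability stays at 1.96% for any m.

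**Step 3. Power on the attempted set.** Assume 12% in implanted subjects and 30% in excluded ones. The combined rate is (27.36 + 0.30·m)/N:

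- m = 5: 28.86/233 = 12.4%, exact power 87%
- m = 12: 30.96/240 = 12.9%, exact power 81%
- m = 25: 34.86/253 = 13.8%, exact power 69%

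With q = 12%, power is 90-91%.

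**Step 4. Can a handful of subjects reverse a result?** Only at the edge. From 33/228, adding 2 attempts with 1 event gives 34/230, exact p = 0.0259, a fail. Adding 5 with 2 gives 35/233, p = 0.0313, and 10 with 3 gives 36/238, p = 0.0329. From 32/228 the same additions all pass (p = 0.017, 0.021, 0.022). Under the null-variance normal test 34/230 passes (p = 0.024), and under a Wald test all three pass (p = 0.013, 0.017, 0.018). If the true rate is 12%, exactly 33 events has probability of about 4%.

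**The case against.** **The direction is not documented.** A reader might infer that the rule certainly lowers TLF_ISR. It does so only if excluded subjects fare worse, which is plausible for failed deliveries but not shown. This stands, so the point is conditional.

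**The rule is per subject.** A reader might infer that every failed attempt or bail-out is lost. It is not: one XIENCE in an ISR target lesion keeps the subject in, even if another attempt failed or a further device was added. Only complete failures leave.

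**The written routes are not device failures.** Stock-out is a supply problem, and balloon-only treatment follows an OCT finding. Where XIENCE was never attempted, an attempted set excludes these subjects too. A reader should not take these provisions as evidence of failed deliveries, which the documents do not quantify. They matter for the arm contrast and for reporting.

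**The SAP text is hidden.** The ISR population and sensitivity paragraphs in SAP Appendix C are redacted. A supportive attempted-treatment analysis may exist, so one cannot say that none is planned.

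**Implanted-only is a legitimate, pre-specified set.** It describes the device once implanted, and protocol 7.1.1.3 likewise restricts MSA to stented subjects. That supports reporting it. It does not make it a sufficient sole basis for a treatment claim against a fixed goal.

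**The arm contrast is only a consistency subgroup.** True. SAP 5.3.7 also has an ISR subgroup for TVF, whose primary population is intention to treat, though for a different endpoint. The remedy can therefore be a label.

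**Conclusion.** The concern holds in conditional form. The visible protocol text makes the goal-test population depend on a result after randomization, and a single cohort has no offsetting control. If subjects with a wholly failed attempt have more events than implanted subjects, TLF_ISR is too favourable. With 5-10% excluded at a 30-40% event rate and a true all-attempted rate of 20%, the exact test passes 3.1-10.8% of the time. At 2% excluded, that range is 2.4-2.9%. With equal event rates there is no effect. These sizes rest on an assumed exact test and on assumed exclusion and event rates.

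A reader might also infer that a few excluded subjects would generally decide the result. The documents do not support that: the reversals in Step 4 need a result at the last passing count, assumed event rates of 30-50%, and in the smallest case the exact test.

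**What to change.** First check whether the redacted SAP Appendix C text already contains an attempted-treatment analysis. If it does not, amend protocol Appendix F and the matching SAP text as follows:

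1. Run the goal test on all randomized subjects with a declared ISR target lesion in whom XIENCE was attempted in that lesion. Count events in that vessel whatever was finally implanted.
2. For this analysis, take the target lesion as the treated segment when no stent was placed, because Appendix B defines it from the stented lesion.
3. Report the implanted-only result beside it.
4. Tabulate the declared-ISR subjects left out, and their TLF, by reason (failed delivery, other DES including stock-out, balloon only) and by arm.
5. Label the OCT-versus-angiography TLF_ISR subgroup in the implanted set as not a comparison of the groups as randomized, or run it on all randomized subjects with a declared ISR target lesion.

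**Cost.** Target lesions are declared before randomization, the 10% ISR cap requires ISR status to be tracked, and randomized subjects are already followed with adjudicated events. The case report form must identify XIENCE attempts per lesion; it is redacted, so this needs checking. The reported rate may be slightly less favourable, and power may fall as in Step 3.
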